Appendix 3. Mayo Scoring System for Assessment of Ulcerative Colitis Activity

Stool Frequency – Each subject serves as his or her own control to establish the degree of abnormality of the stool frequency	0	Normal number of stools for subject
	1	1 to 2 stools per day more than normal
	2	3 to 4 stools more than normal
	3	≥ 5 stools more than normal
Rectal Bleeding - The daily bleeding score represents the most severe bleeding of the day	0	No blood seen
	1	Streaks of blood with stool less than half the time
	2	Obvious blood with stool half or more than half of the time
	3	Blood alone passes
Endoscopic findings - Assessed by Central Reader (include only for MCS assessment)	0	Normal or inactive disease
	1	Mild Disease (erythema, decreased vascular pattern)
	2	Moderate Disease (marked erythema, lack of vascular pattern, friability, erosions)
	3	Severe Disease (spontaneous bleeding, ulceration)
Physician’s Global Assessment - The physician’s global assessment acknowledges the three other criteria, the subject’s daily recollection of abdominal discomfort and general sense of wellbeing, and other observation, such as physical findings and the subject’s performance status.	0	Normal
	1	Mild disease
	2	Moderate disease
	3	Severe disease

Appendix 4. Mayo Clinic Score (MCS) Calculation

Definition of the Mayo Clinic Score and Component Subscores

The Mayo Clinic Score (MCS) is a composite index of 4 disease activity variables; stool frequency, rectal bleeding, endoscopic findings, and the physician global assessment (PGA) . Each of the 4 variables is assigned an integer subscore from 0-3 as described in [Table 6-2](#).

- The MCS is calculated as the sum of the 4 subscores for stool frequency, rectal bleeding, endoscopic findings, and the PGA.
- Partial MCS (pMCS) is the sum of the 3 subscores for stool frequency, rectal bleeding, and the PGA.
- EBS (Endoscopy, Bleeding, Stool Frequency) is a description of the 3 subscores for endoscopic findings, rectal bleeding, and stool frequency.

Calculation of Mayo Clinic Score and Component Subscores

In the GS-US-418-3898 study, subjects report daily stool frequency and rectal bleeding symptoms on the study Logpad (an electronic medical diary). The physician reports the PGA at specified visits on the study Sitepad. Results of endoscopic evaluation are reported by a central reader and site personnel enters the score on the Sitepad.

For the purposes of calculation of the specific MCS and component subscores an anchor date is assigned and stool frequency and rectal bleeding records prior to the anchor date are used in the calculation of the subscores.

For screening calculations of MCS and EBS, the anchor date is considered the date of the endoscopy. As endoscopic subscore will be only evaluated over screening and not at Day 1 baseline. Screening MCS and EBS will be used as baseline evaluation.

For all calculations at other visits, including baseline partial MCS, postbaseline MCS, EBS, and partial MCS, the anchor date is the date of the study visit.

Because the preparation for endoscopy procedure may impact the validity of the diary data, the patients reported daily stool frequency and rectal bleeding records collected 1 day prior to, the day of, and the day after the procedure will not be used in the calculation of stool frequency and rectal bleeding subscores. These above mentioned days are considered as non-evaluable days for those 2 subscores.

[figure not shown]
Calculation of MCS and EBS at Screening/Baseline

The calculation of the screening stool frequency subscore and screening rectal bleeding subscores for the purposes of calculation of baseline MCS and baseline EBS is as follows:

- 1) The endoscopic procedure date is defined as the E-Day 1.
- 2) A 7-day window is defined in which the start of the window begins 7 days prior to the endoscopic procedure date and the window ends on the day prior to the endoscopic procedure date.
- 3) The subscore is calculated as the average of the 3 evaluable dairy data entries within the 7-day window closest to the endoscopic procedure date (discarding the day prior to endoscopy) and rounded to the nearest integer.
- 4) If a subject does not have 3 evaluable diary day entries within the 7-day window, this subject will have a missing subscore and missing baseline MCS and EBS.
- 5) The PGA subscore used in the baseline MCS is that recorded during the screening period (prior to Day1) .

A schema of this approach ([Appendix Figure 1](#)) and examples are included below in [Appendix Table 1](#):

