3.8. Analysis Visit Windows

3.8.1. Definitions

3.8.1.1. Induction Studies (Cohort A Induction Study and Cohort B Induction Study)

The First Dosing Date of each Induction Study is defined as the date when subjects take the first dose of Induction study drug, as recorded in the Study Drug Administration eCRF.

The Last Dosing Date of each Induction Study is defined as the date when subjects take the last dose of Induction study drug as recorded in the Study Drug Administration eCRF.

Study Day will be calculated from the first dosing date of study drug and derived as follows:

- For days on or after first dosing date: Assessment Date - First Dosing Date + 1
- For days prior to the first dosing date: Assessment Date - First Dosing Date

Therefore, Study Day 1 is the day of the first dose of study drug administration.

Baseline is defined as the last available observation on or prior to the first dosing date, unless otherwise specified.

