6. EFFICACY ANALYSES

6.1. General Considerations

The efficacy analysis will be conducted on the FAS, defined in Section 3.1.2, unless otherwise specified.

The definitions of the dichotomous efficacy endpoints for each individual study (Cohort A Induction Study, Cohort B Induction Study, and Maintenance Study) are listed in Table 6-1. While the endoscopic appearance will be read by both study site investigator and central reader, only the centrally-read endoscopic subscore will be used in the calculations of Mayo Clinic Score (MCS) and other related efficacy endpoints unless otherwise stated.

Appendix 5 includes a detailed definition of study treatment failure and the corresponding data handling rules for efficacy analysis.

Table 6-1. Definitions of Dichotomous Efficacy Endpoints

Study	Type	Event Endpoint	Definition
Induction	Primary	EBS remission at Week 10	An endoscopic subscore of 0 or 1*, rectal bleeding subscore of 0, and at least a 1 point decrease in stool frequency from baseline to achieve a subscore of 0 or 1 at Week 10
Induction	Key Secondary	MCS remission at Week 10	A MCS of 2 or less and no single subscore higher than 1 at Week 10
Induction	Key Secondary	An endoscopic subscore of 0 at Week 10	An endoscopic subscore of 0 at Week 10
Induction	Key Secondary	Geboes histologic remission at Week 10	Based on the Geboes Scale (Appendix 6), all of the following must be met to be considered in Geboes histologic remission at Week 10: Grade 0 of ≤ 0.3 , Grade 1 of ≤ 1.1 , Grade 2a of $\leq 2A.3$, Grade 2b of 2B.0, Grade 3 of 3.0, Grade 4 of 4.0, and Grade 5 of 5.0 {Geboes 2000}.
Induction	Key Secondary	MCS remission (alternative definition) at Week 10	Rectal bleeding, stool frequency, and PGA subscore of 0 and an endoscopic subscore of 0 or 1; overall MCS of ≤ 1 at Week 10
Induction	Exploratory	Novel histologic outcomes at Week 10	This novel histologic outcome incorporates both Geboes and non-Geboes criteria. Based on the Geboes Scale (Appendix 6), all of the following must be met to achieve the following novel, exploratory histologic outcome at Week 10: Grade 0 of ≤ 0.3 , Grade 1 of ≤ 1.1 , Grade 2a of 2A.0, Grade 2b of 2B.0, Grade 3 of 3.0, Grade 4 of 4.0 and Grade 5 of 5.0, along with the absence of basal plasmacytosis.
Induction	Exploratory	EBS remission (alternative definition) at Week 10	An endoscopic subscore of 0 or 1*, rectal bleeding subscore of 0, and stool frequency subscore of 0 or 1 at Week 10

Study	Type	Event Endpoint	Definition

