Maintenance	Exploratory	Novel histologic outcomes at Week 58	This novel histologic outcome incorporates both Geboes and non-Geboes criteria. Based on the Geboes Scale (Appendix 6), all of the following must be met to achieve the following novel, exploratory histologic outcome at Week 58: Grade 0 of ≤ 0.3 , Grade 1 of ≤ 1.1 , Grade 2a of 2A.0, Grade 2b of 2B.0, Grade 3 of 3.0, Grade 4 of 4.0 and Grade 5 of 5.0, alone with the absence of basal plasmacytosis.

Study	Type	Event Endpoint	Definition
Maintenance	Exploratory	EBS remission (alternative definition) at Week 58	An endoscopic subscore of 0 or 1*, rectal bleeding subscore of 0, and stool frequency subscore of 0 or 1 at Week 58
Maintenance	Exploratory	MCS response at Week 58	An MCS reduction of ≥ 3 points and at least 30% from induction baseline score with an accompanying decrease in rectal bleeding subscore of ≥ 1 point or an absolute rectal bleeding subscore of 0 or 1 at Week 58
Maintenance	Exploratory	Endoscopic response at Week 58	An endoscopic subscore of 0 or 1 at Week 58

* Based on centrally read endoscopy.

MCS response will be used as one of the response criteria at Week 10 to decide whether subjects are eligible to be re-randomized into Maintenance Study.

Endoscopic response will be evaluated at the futility analysis at the second DMC meeting.

Summary of Dichotomous Efficacy Endpoints

For the Cohort A Induction Study, the Cohort B Induction Study, and the Maintenance Study, numbers and percentages of subjects achieving each of the dichotomous efficacy endpoints defined above, and numbers and percentages of subjects not achieving those endpoints for the following reasons will be summarized by treatment.

- 1) Subjects who are observed non-responders;
- 2) Subjects who are non-responders due to study treatment failure
- 3) Subjects who are non-responders due to study drug discontinuation led by protocol-specified disease worsening (maintenance study only)
- 4) Subjects who do not have sufficient measurements to determine the endpoint due to study drug discontinuation for other reasons
- 5) Subjects who do not have sufficient measurements to determine the endpoint while on study drug

Non-Responder Imputation (NRI)

For analysis of all the above defined efficacy endpoints, subjects who do not have sufficient measurements to determine the endpoint will be considered non-responders (ie, non-responder imputation [NRI]).

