6.2. Primary Efficacy Endpoints

6.2.1. Definition of the Primary Efficacy Endpoints

The primary efficacy endpoints are the proportion of subjects achieving EBS remission at Week 10 for the Induction Studies (Cohort A Induction Study and Cohort B Induction Study) and at Week 58 for Maintenance Study as defined in Table 6-1. MCS subscores collected at screening will be used as baseline values for evaluation of EBS remission at both Week 10 and Week 58.

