6.4.2.2. Analysis of MCS and pMCS exploratory endpoints

For calculation of MCS and pMCS, please refer to rules described under [Section 6.1.1](#) for MCS and pMCS with subscores.

MCS at screening will serve as induction baseline MCS. Partial MCS at Day 1 will serve as induction baseline pMCS. If pMCS at Day 1 is missing, the screening partial MCS will be used as induction baseline.

MCS at Week 10 will serve as maintenance re-baseline MCS. Partial MCS at Maintenance Day 1 will serve as Maintenance re-baseline pMCS. Re-baseline values of MCS and partial MCS will serve as Maintenance Study baseline for change from baseline calculation.

As 2 of the 3 partial MCS components (stool frequency and rectal bleeding) will be collected through the subject daily diary, partial MCS will be calculated at all visits when PGA is scheduled to be assessed.

Descriptive statistics will be used to summarize the absolute values and change from baseline values in MCS, endoscopic subscore, stool frequency subscore, rectal bleeding subscore, PGA and partial MCS by analysis visit and treatment group for Cohort A Induction Study, Cohort B Induction Study, and Maintenance Study. Shift tables of MCS subscores from baseline to Week 10 for Induction Studies and from Week 10 to Week 58 for Maintenance Study will be provided.

Difference of mean change from baseline at Week 10 for Induction Studies and difference of mean change from re-baseline at Week 58 for Maintenance study between each filgotinib dose group and placebo for partial MCS will be tested in an exploratory fashion using an analysis of covariance (ANCOVA) model adjusting for stratification factors and baseline or rebaseline value, respectively. Last Observation Carried Forward (LOCF) approach will be used to impute the missing values. Estimated means of treatment effects and estimated differences in treatment effects between each filgotinib treatment group and the placebo group will be presented with 95% CIs and nominal p-values. Difference of mean change from baseline (or re-baseline) for partial MCS at Weeks 2, 4, and 6 for Induction Studies and at Weeks 14, 20, 26, 34, 42 and 50 for Maintenance Study will be analyzed in the same fashion. The model based estimated mean change from baseline (or re-baseline) with 95% CIs will be plotted over all analysis visits by treatment group.

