Appendix Figure 1. Stool Frequency and Rectal Bleeding Subscores Calculations at Screening

Appendix Table 1. Examples of Calculations for the Rectal Bleeding and the Stool Frequency Subscores of MCS and EBS at Baseline

Example	Diary Day Looking Back from Endoscopy Date							Anchor Day	Days for Calculation	Average Subscore	Final Subscore
	-7	-6	-5	-4	-3	-2	-1	E-Day 1			
	3 Jun	4 Jun	5 Jun	6 Jun	7 Jun	8 Jun	9 Jun	10 Jun			
Diary 1	M	M	2	M	1	2	X	X	2, 3, 5	1.67	2
Diary 2	M	M	M	M	0	1	X	X	2, 3	Missing	Missing
Diary 3	M	M	M	M	0	M	X	X	3	Missing	Missing
Diary 4	M	2	M	2	1	1	X	X	2, 3, 4	1.33	1

Days are named relative to Anchor Day Endoscopy Date (E Day 1), M Missing, X non evaluable
 The diary data collected on E Day 1 and E Day 1 will be discarded as endoscopy and its preparation may impact the validity of the diary data.

[figure not shown]
Calculation of Partial MCS at Baseline, and Postbaseline MCS, EBS, and Partial MCS

The calculation of baseline partial MCS and postbaseline MCS, EBS and partial MCS use the study visit date as the anchor date. For baseline pMCS, the visit date is the Day 1 visit. The calculations are as follows:

- 1) Subject diary data collected within 7 days prior to the visit day will be used for calculation, and some of the days within this 7-day window may be considered non-evaluable due to the endoscopy procedure and its preparation (ie, the day of the endoscopy and the day prior to the endoscopy).
- 2) The average of the 3 evaluable diary day entries within the 7-day window closest to the visit day (V-Day 1), rounded to the nearest integer, will be considered the stool frequency and rectal bleeding subscore for that visit
- 3) The PGA subscore used in the calculation of baseline partial MCS is the PGA subscore recorded on Day 1. At subsequent visits, the PGA subscore used in calculation of MCS and partial MCS is that recorded within the visit window
- 4) If there are 2 or less evaluable diary day entries for stool frequency or rectal bleeding within the 7-day window, no missing data imputation will be done. MCS, EBS and partial MCS will be considered as missing.
- 5) For MCS, if endoscopic subscore or PGA subscore is missing, MCS will be left as missing. For Partial MCS, if PGA is missing, partial MCS will be left as missing.

A schema of this approach and some examples are included below in [Appendix Figure 2](#) and [Appendix Table 2](#):

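### A subject with too few screening diary entries has no EBS or MCS baseline, so counts as a Week 10 non-responder and drops out of the Maintenance FAS; a Day 1 fallback would recover some of these subjects

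*SAP*

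**What the plan says.** **Short screening diary.** SAP Appendix 4, step 4 of the screening/baseline calculation: "If a subject does not have 3 evaluable diary day entries within the 7-day window", then "this subject will have a missing subscore and missing baseline MCS and EBS". No substitute is given. Diaries 2 and 3 in Appendix Table 1 illustrate the rule.

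**Baseline for the primary endpoint.** SAP Section 3.8.1.1 sets a general rule: "Baseline is defined as the last available observation on or prior to the first dosing date, unless otherwise specified". Section 6.2.1 specifies otherwise for EBS: "MCS subscores collected at screening will be used as baseline values for evaluation of EBS remission at both Week 10 and Week 58". Protocol Section 8.5.1 also names screening as the baseline.

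**Endpoint.** SAP Table 6-1 requires, among other things, "at least a 1 point decrease in stool frequency from baseline to achieve a subscore of 0 or 1 at Week 10". MCS response is likewise defined by a reduction from baseline MCS. MCS remission, endoscopic subscore of 0 and Geboes remission at Week 10 use no baseline.

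**Undeterminable endpoints.** SAP Section 6.1: "subjects who do not have sufficient measurements to determine the endpoint will be considered non-responders".

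**Maintenance FAS.** SAP Section 3.1.2 admits only subjects who reached EBS remission or MCS response at Week 10 under the SAP's own rules.

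**Day 1 diary subscores.** Appendix 4 derives them for baseline partial MCS: "For baseline pMCS, the visit date is the Day 1 visit". Section 6.4.2.2 has a fallback in the other direction: "If pMCS at Day 1 is missing, the screening partial MCS will be used as induction baseline".

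**The concern.** A gap in a pre-treatment diary can decide a primary-endpoint classification whatever the outcome at Week 10. A subject with endoscopy, bleeding, stool frequency and PGA all at 0 at Week 10 counts as a success for MCS remission, a key secondary endpoint, and as a non-responder for EBS remission, the primary endpoint.

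The consequence carries forward. Because the subject is also a non-responder for MCS response, a re-randomised and dosed subject is removed from every Maintenance efficacy analysis based on the FAS.

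The planned sensitivity analyses do not cleanly repair this:
- Observed-cases (Section 6.2.4.3) requires baseline data.
- The per-protocol sets (Section 3.1.3) require enough data to evaluate EBS remission, or a qualifying treatment failure.
- The multiple-imputation model uses the baseline EBS subscores as predictors and has no rule for when they are missing.

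**Working it through.** **1. Trace one subject.** Fewer than three evaluable screening entries; every Week 10 subscore is 0; no treatment failure.

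| Outcome | Baseline needed? | Result under the SAP |
|---|---|---|
| MCS remission, Week 10 | No | Responder |
| Endoscopic subscore of 0, Week 10 | No | Responder |
| EBS remission, Week 10 | Yes, stool frequency | Not determinable, so non-responder |
| MCS response, Week 10 | Yes, MCS | Not determinable, so non-responder |
| Maintenance FAS | Yes, through the two rows above | Excluded |

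**2. Reproduce the plan's power (SAP Section 1.3).** Induction inputs: 130 placebo, 260 per dose, 10% v 25%, 2-sided 0.025 (z = 2.241).

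Power = Φ[(d − z·SE0)/SE1], with SE0 from the pooled rate and SE1 from the separate rates.
- Pooled rate = (130×0.10 + 260×0.25)/390 = 0.20.
- SE0 = √[0.20×0.80×(1/130 + 1/260)] = 0.0430.
- SE1 = √[0.10×0.90/130 + 0.25×0.75/260] = 0.0376.
- Power = Φ[(0.15 − 2.241×0.0430)/0.0376] = Φ(1.43) = 92.3%.

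With a continuity correction the same inputs give 89.9%, which reproduces the stated 90%. Maintenance (95 v 190, 20% v 40%) gives 89.2% uncorrected and 86.3% corrected, both consistent with the plan's claim of more than 85%. The uncorrected form is used below. Using the operative Induction level of 0.02499 instead of 0.025 leaves 92.3% unchanged to one decimal.

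**3. Effect of the rule.** Let m be the share of subjects without a screening baseline. The documents do not give m; 1% to 3% is assumed, the same in every arm and unrelated to outcome. In Induction the rates become 25%×(1−m) and 10%×(1−m). In Maintenance the rates stay and the numbers become 190×(1−m) and 95×(1−m), because the subject is excluded.

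| m | Induction rates | Induction power | Maintenance power |
|---|---|---|---|
| 0% | 25.0% v 10.0% | 92.3% | 89.2% |
| 1% | 24.8% v 9.9% | 92.0% | 88.9% |
| 2% | 24.5% v 9.8% | 91.6% | 88.5% |
| 3% | 24.3% v 9.7% | 91.2% | 88.2% |

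At m = 2%, 650×0.02 = 13 subjects per cohort are affected. True remitters lost are 260×0.02×0.25 = 1.3 per filgotinib arm and 130×0.02×0.10 = 0.26 on placebo.

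**4. What a Day 1 fallback could add.** The Study Procedures Table allows screening endoscopy on Day −14 to −1. The Day 1 window is Day −7 to −1, less the endoscopy day and the day either side. The table counts evaluable days that the screening window did not already contain.

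| Screening endoscopy | New evaluable diary days |
|---|---|
| Day −14 to −9 | 7 |
| Day −8 | 6 |
| Day −7 | 5 |
| Day −6 | 4 |
| Day −5 | 3 |
| Day −4 | 2 |
| Day −3 | 1 |
| Day −2 or −1 | 0 |

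For endoscopy on Day −14 to −5 there are at least three new days, enough on their own for a subscore if the diary was completed.

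**The case against.** **The group should be almost empty.** Entry requires diary-based rectal bleeding and stool frequency scores of at least 1, and Protocol Section 6.2.1 tells sites not to perform endoscopy until the diary criteria are met. This stands, and it is why the point is minor. It does not make the group impossible: eligibility MCS is calculated centrally during the study, while the SAP recalculates the scores and does not use the vendor's. The documents do not say that the two calculations always agree.

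**The baseline can be inferred.** One could argue that stool frequency of 0 at Week 10 in an eligible subject must be a fall of at least one point. The SAP does not provide for that inference, and it rests on the same diary that is short, so it is not relied on here.

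**A single screening baseline is deliberate.** Both documents name it, and the only fallback precedent is for an exploratory endpoint. True, but the reason given in Appendix 4 is that endoscopy is done at screening and not at Day 1. That does not apply to stool frequency and bleeding, which have diary entries before Day 1 as well.

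**Existing outputs expose the issue.** Section 6.1 tabulates reasons for non-response, Section 6.2.4.3 summarises missing EBS by treatment group and includes missing-as-success analyses, and an exploratory alternative EBS definition needs no baseline. These help, but the listed reasons do not separate a missing baseline from a missing Week 10 assessment.

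**Stronger readings that the documents do not support.** A reader might infer that the subject is also scored a failure at Week 58, since the same screening baseline applies there. Section 3.1.2 rules that out by excluding the subject from the Maintenance FAS. Nor do the two missing results among the four examples in Appendix Table 1 say anything about frequency; they are illustrations.

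**Conclusion.** The point holds as a small gap in the plan. Taken literally, the SAP makes a subject with a short screening diary a Week 10 non-responder for EBS remission and MCS response whatever the Week 10 findings, and excludes that subject from the Maintenance FAS.

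The size rests on an assumed frequency. At 1% to 3%, uncorrected power falls by 0.3 to 1.1 points in Induction (92.3% to 92.0–91.2%) and by 0.3 to 1.0 points in Maintenance (89.2% to 88.9–88.2%).

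No type I error inflation is expected. The screening diary precedes the first dose, the rule is blind to treatment, and the Maintenance exclusion turns on information fixed before re-randomisation. The effect is a slight shrinkage of the Induction difference and a slight loss of Maintenance subjects. It is worth correcting because the correction is cheap, not because the trial's conclusions are at risk.

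**What to change.** Add to step 4 of the screening calculation in SAP Appendix 4: if the screening stool frequency or rectal bleeding subscore is missing, use the pre-dose Day 1 subscore already derived for partial MCS as the baseline; treat the baseline as missing only when both are missing.

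State that this applies to EBS remission, MCS response, the Maintenance FAS and the multiple-imputation model, and cross-refer to it in Section 6.2.1. Report by arm how many subjects used the fallback and how many still lack a baseline.

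**Cost.** One SAP sentence, a cross-reference and one summary line; the Day 1 subscores are already specified. For the few subjects concerned the baseline comes from a slightly different date. The remedy is partial: it adds no new diary days when screening endoscopy falls on Day −2 or −1, and only one or two on Day −3 or −4.
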